6. STUDY TREATMENTS

6.1. Treatments Administered

6.1.1. KPT-9274

KPT-9274 is an orally bioavailable small molecule prepared in a tablet solid dosage form for oral administration.

KPT-9274 tablets are designed for immediate-release oral administration and will be supplied in high-density polyethylene (HDPE) bottles with induction seals and polypropylene caps.

KPT-9274 tablets will be film coated for ease of handling and provided in tablet strengths of 5 mg and 20 mg. KPT-9274 will be supplied by Karyopharm. Additional details on KPT-9274 are provided in the IB. The investigational treatments will be administered as a flat dose and not by body weight or body surface area.

6.1.2. Niacin ER (Part B)

Patients enrolled in Part B of the Dose Escalation Phase or in the Dose Expansion cohort with co-administration of niacin will also receive 500 mg of any FDA approved prescription, generic niacin ER for oral use co-administered with each dose of KPT-9274. The starting dose of 500 mg niacin ER may be titrated up to 2,000 mg of daily dose, per label. A list of approved generic niacin ER will be provided in the Pharmacy Manual. The niacin ER study treatment will be obtained by the site pharmacy.

6.1.3. Nivolumab (Part C)

Nivolumab will begin on the first day (C1D1) and will be administered through an intravenous (IV) line on Day 1 of each cycle (once every 4-week cycle) at 480 mg according to the current prescribing information. Nivolumab will be given per standard of care.

All dosages prescribed to the patient and all dose changes during the study must be recorded on the eCRF.

6.1.4. Placebo or Control

Not applicable. This is not a placebo-controlled study and the active treatment will not be compared to a control treatment.

6.2. Study Treatment Dose Schedules and Administration

6.2.1. Labeling

All labels will include conditions for storage, lot number, and other pertinent information such as Sponsor and a caution statement. Medication labels for KPT-9274 will be in the local language of the site and comply with the legal requirements of each country.

6.2.2. Dispensing Directions

The Investigator or responsible site personnel must instruct the patient or caregiver to take the study treatment(s) as per protocol. Study treatment(s) will be dispensed to the patient by authorized site personnel only.

6.2.3. Dosing Information

Patients will receive oral KPT-9274 three times a week every other day (Days 1, 3, 5, 8, 10, 12, 15, 17, 19, 22, 24, and 26) during each 28-day cycle.

Study treatment will be administered in the clinic and at home as indicated in [Table 4](#). Study treatment dosing will occur in the clinic during Cycle 1 on Days 1, 3, 8, 15, 22, 24, and 26, during Cycle 2 on Days 1, 8, 15, and 22, and during \geq Cycle 3 on Days 1 and 15. Study treatment dosing will occur at home during Cycle 1 on Days 5, 10, 12, 17, and 19, during Cycle 2 on Days 3, 5, 10, 12, 17, 19, 24, and 26 and during Cycles \geq 3 on Days 3, 5, 8, 10, 12, 17, 19, 22, 24, and 26.

During Part B of the Dose Escalation Phase, patients will receive 500 mg niacin ER co-administered with each dose of KPT-9274. The starting dose of 500 mg niacin ER may be titrated to 2,000 mg of daily dose, per label. The starting dose for KPT-9274 in Part B will be a dose and schedule that cleared DLT assessment during Part A. For the purposes of dose escalation decisions, a standard 3+3 dose escalation design will be used during both Part A and Part B.

A total of ~65 patients with advanced solid malignancies and NHL may be enrolled to further explore safety, tolerability and preliminary evidence of anti-tumor activity of the RP2D of KPT-9274 \pm niacin ER. After declaring the RP2D \pm niacin ER (see Section [6.2.6](#)), based on the safety and tolerability results of the Dose Escalation Phase, a decision will be made whether expansion (4 groups, ~45 patients total) will be conducted at the RP2D of KPT-9274 single agent or at the RP2D of KPT-9274 + niacin ER. If the 45 patient expansion is conducted at the RP2D of KPT-9274 + niacin ER, an optional expansion with < 20 patients at the RP2D of KPT-9274 single agent may be initiated. Futility analyses based on clinical efficacy will be conducted in a maximum of 10 patients dosed at the RP2D \pm niacin ER (see Section [6.2.7](#) for additional details).

Dose escalation will occur according to the Dose Escalation Guidelines provided in Section [6.2.6](#).

Patients with melanoma enrolled in Part C, KPT-9274 + nivolumab, cohort will receive nivolumab (480 mg once per 28 day cycle) according to the current prescribing information.

6.2.4. Dosing Instructions for Patients

Study medications will be dosed according to the schedules provided in [Table 4](#). For doses of oral medication to be taken on non-clinic days, patients will be provided with an adequate supply of study treatment for self-administration at home until at least their next scheduled study visit. Patients will be provided with a take home diary to complete on home dosing days; the patient diary will be reviewed at each clinic visit.

Oral KPT-9274 should be given with food, or within 30 minutes after the patient has eaten, together with 240-355 mL (8-12 ounces) of fluids.

KPT-9274 tablets should be swallowed whole (not crushed).

Nivolumab (anti-PD-1) will be administered at the site based on the product label.

6.2.5. Dose Schedules for Evaluation During the Dose Escalation Phase

The dose schedule for evaluation during the Dose Escalation Phase in Part A is presented in [Table 13](#). A similar dose escalation plan will be used in Part B; however, the starting dose of KPT-9274 will be a dose and schedule that has cleared DLT assessment during Part A.

To better evaluate the safety, tolerability, and PK of KPT-9274, additional cohorts of patients may be enrolled on alternate dosing schedules (e.g. dosing on 2 days per week), at preceding dose levels, or to intermediate dose levels before or while proceeding with further dose escalation. Assessments at clinic visits may need to be adjusted based on the dosing schedule.

Table 13: Part A - KPT-9274 Dose Escalation Levels

Cohort	KPT-9274
	Days 1, 3, 5, 8, 10, 12, 15, 17, 19, 22, 24, 26 in a 28-day cycle
1 (starting dose)	10 mg
2	20 mg
3	30 mg
4	40 mg
5+	Increases at 20 mg per cohort

Three patients will be enrolled in each cohort, if 1 of 3 patients in a cohort experiences a DLT, the number of patients in that cohort will be expanded to 6 patients. A maximum of 6 patients will be enrolled per cohort. If ≥ 2 patients in a cohort experience a DLT, the MTD will be defined as 1 dose level lower.

6.2.6. Dose Escalation Guidelines

6.2.6.1. Dose Escalation Procedures

The Dose Escalation Phase will include two parts, Part A and Part B.

- Part A will be performed to determine the RP2D and MTD of KPT-9274 alone (note that the RP2D may be \leq the MTD and will be used for the Dose Expansion Phase of the study).
- Part B will be performed to determine the RP2D and MTD of KPT-9274 co-administered with a starting dose of 500 mg niacin ER (and may be titrated up to 2,000 mg daily dose, per label); the starting dose of KPT-9274 for Part B will be a dose and schedule that has cleared DLT assessment in Part A.

For the purposes of dose escalation decisions for both Part A and Part B, a standard 3+3 dose escalation design will be used. Based on preclinical and early clinical data, patients will be enrolled according to their NAPRT1 status at a ratio of 2:1 (NAPRT1 negative:NAPRT1

positive). The NAPRT1 status must be determined prior to enrollment based on evaluation of a fresh tumor biopsy or archival tissue taken \leq 6 months of screening.

Part A (KPT-9274 single agent):

The initial cohort, Cohort 1, will consist of 3 enrolled patients who will be treated at 10 mg. If these patients do not experience a DLT during Cycle 1, the KPT-9274 dose will be escalated to 20 mg for another group of 3 patients (Cohort 2) upon approval during a dose decision meeting. Dose escalation will continue based on a standard 3+3 design at the dose levels specified in the [Table 13](#) and as further described for both parts below.

Part B (KPT-9274 + niacin ER):

The initial cohort, Cohort 1 + niacin ER (Cohort 1B), will consist of 3 enrolled patients who will be treated at a dose and schedule of KPT-9274 that has cleared DLT assessment in Part A, co-administered with a starting dose of 500 mg niacin ER (and may be titrated to 2,000 mg daily dose, per label) with each dose of KPT-9274.

Part A and Part B:

Dose escalation will continue independently in Parts A and B until the MTD in each part is determined. A RP2D equal to or less than the MTD will be declared for each part and used for the Dose Expansion Phase. The MTD is defined as the highest dose at which \leq 1 patient experiences a DLT in Cycle 1.

Patients must complete a minimum of 1 cycle of treatment, defined as receiving \geq 75% of KPT-9274 doses during Cycle 1 (e.g., \geq 9 of 12 doses in the 3 doses/week schedule), or have a DLT within the first cycle of treatment to be evaluable for dose escalation decisions. Dose escalation decisions will occur when the cohort of patients has met these criteria.

Dose escalation decisions will be made by enrolling Investigators and Karyopharm study personnel. Decisions will be based on an evaluation of all relevant data available from all dose levels evaluated in the ongoing study including safety information, DLTs, all CTCAE (Version 4.03) toxicity data during Cycle 1 and PK data (if available) from evaluable patients (see Section [6.2.6.3](#))

[Table 13](#) describes the starting dose and the dose cohorts that may be evaluated in Part A. A similar dose escalation plan will be used in Part B. To better evaluate the safety, tolerability and PK of KPT-9274, additional cohorts of patients may be enrolled on alternate dosing schedules, at preceding dose levels, or to intermediate dose levels before or while proceeding with further dose escalation.

Dose escalation for Part A and Part B will be conducted as follows:

- If 0 of 3 patients experiences a DLT, escalate to next higher dose cohort.
- If 1 of 3 patients experiences a DLT, that cohort will be expanded to 6 patients. If 1 of 6 patients experiences a DLT, escalate to the next higher dose cohort;
- If \geq 2 of 3 or \geq 2 of 6 patients experience a DLT, MTD is exceeded. If the MTD is exceeded, the patients will be de-escalated to the next lower dose level (the MTD).

Part C (KPT-9274 + nivolumab):

The initial cohort will consist of 3 enrolled patients who will be treated at a dose of 30 mg KPT-9274, co-administered with a dose of 480 mg nivolumab. If these patients do not experience a DLT during Cycle 1, the KPT-9274 dose will be escalated to 40 mg for another cohort of 3 patients upon approval during a dose decision meeting. A maximum of 10 patients may be enrolled at each dose level.

Additional KPT-9274 dose levels (e.g., 20 mg or 60 mg) may be evaluated if an optimal dose is not identified and the safety review committee is in agreement.

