3.2. Replacement Policy

Patients who complete the first cycle of therapy will not be replaced during the Escalation Phase of the study. However, if a patient is considered as non-evaluable for DLT (i.e., did not complete the first cycle of therapy and did not experience a DLT), enrollment of a new patient to the current cohort will be considered if there is less than the required number of evaluable patients.

During the Dose Expansion Phase, patients who have not completed 1 cycle will be replaced unless they were discontinued from the study due to a drug-related toxicity, PD, or death.

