3.3. Treatment Duration

Treatment cycles are 28 days long. A patient may continue to receive KPT-9274 until that patient experiences PD, withdraws consent, is lost to follow-up, experiences intolerable toxicity which precludes further treatment with KPT-9274, or treatment is discontinued at the discretion of the Investigator or the Karyopharm Medical Monitor.

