6.2.6.2. Dose-Limiting Toxicity

A DLT is defined as an AE or abnormal laboratory value that occurs within the first 28 days of treatment with KPT-9274, except for those that are clearly and incontrovertibly due to underlying disease, disease progression, or extraneous causes, and meets any of the criteria included in [Table 14](#). The CTCAE, Version 4.03 will be used for grading. In addition, > 3 missed (consecutive or non-consecutive) doses of KPT-9274 in the first 28 days due to a drug related toxicity will be considered to be a DLT.

Other events may occur which do not meet the definition of a DLT, but are of concern to the Investigators and Karyopharm, and may then be considered to be DLTs.

Table 14: Criteria for Defining Dose-Limiting Toxicities

Toxicity	Any of the following criteria (based on CTCAE [Version 4.03]):
Non-Hematologic	Grade \geq 3 nausea/vomiting, dehydration or diarrhea while taking optimal supportive medications.
	Any other Grade \geq 3 non-hematological toxicity except alopecia or electrolyte abnormalities correctable with supportive therapy.
Hematologic	Grade 4 neutropenia lasting more than 5 days.
	Febrile neutropenia of any duration (ANC $< 1.0 \times 10^9$ with single temperature $> 38.3^{\circ}\text{C}$ or a sustained temperature $\geq 38^{\circ}\text{C}$ for more than 1 hour).
	Grade 4 thrombocytopenia, or Grade 3 thrombocytopenia with bleeding, or any requirement for platelet transfusion.
	Grade 4 anemia, unexplained by underlying disease.

CTCAE Version 4.03 will be used for grading AEs and laboratory abnormalities. Patients may receive supportive care as per local institutional guidelines.

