9.8. Safety Analysis

All safety analyses will be made on the Safety Population. Details of the analyses will be described in the SAP.

The safety and tolerability of KPT-9274 ± niacin ER will be evaluated by means of DLTs, AE reports, physical examination results, electrocardiogram results and laboratory safety evaluations. NCI CTCAE, Version 4.03 will be used for grading of AEs.

The MTD will be based on the assessment of DLTs during the first cycle of therapy and will be defined as the highest dose at which ≤ 1 patient experiences DLTs within Cycle 1. If the true DLT rate is 33% for each dose cohort, the probability of halting dose escalation at a given dose cohort is 0.57.

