# **DLT Evaluable Population**

All patients who complete a minimum of 1 cycle of treatment, defined as having received  $\geq$  75% of KPT-9274 doses during Cycle 1 (e.g.,  $\geq$  9 of 12 doses in the 3 doses/week schedule), or who have a DLT within the first cycle of treatment, will be included in the DLT evaluable population.

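### DLT evaluability rests on dose count alone, reached as early as Day 19, so a patient who leaves before Day 28 can be counted as DLT-free without adequate follow-up

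*Protocol*

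**What the plan says.** **Window.** Protocol 6.2.6.2: "A DLT is defined as an AE or abnormal laboratory value that occurs within the first 28 days of treatment with KPT-9274". Protocol 3.3: "Treatment cycles are 28 days long".

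**Evaluability.** Protocol 6.2.6.1 asks for a minimum of one cycle of treatment and defines that as at least 75% of the Cycle 1 doses; its example reads, in part: "9 of 12 doses in the 3 doses/week schedule), or have a DLT within the first cycle of treatment to be evaluable for dose escalation". The synopsis, Protocol 9.3.5 and SAP 1.1 carry the same rule. So does SAP 3.1.2, whose DLT-evaluable set begins: "All patients who complete a minimum of 1 cycle of treatment, defined as having received". None of these places adds a minimum time under observation.

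**Timing of the decision.** Protocol 6.2.6.1: "Dose escalation decisions will occur when the cohort of patients has met these criteria".

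**Replacement.** Protocol 3.2 treats a patient as non-evaluable, and so potentially replaceable, if he or she "did not complete the first cycle of therapy and did not experience a DLT".

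**Operating characteristic.** Protocol 9.8 states that, at a true DLT rate of 33%, "the probability of halting dose escalation at a given dose cohort is 0.57".

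**The concern.** The event is defined over 28 days, but membership of the denominator is defined by doses taken. The two do not end on the same day. A patient who takes nine doses and then withdraws consent, starts another anticancer therapy or stops the drug permanently satisfies the definition. On the 75% definition of a completed cycle, that patient is also not replaced.

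What is collected afterwards may be too thin to say that no DLT occurred:

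- Protocol 8.1.2 ends non-serious AE reporting when new antineoplastic therapy starts.
- Protocol Table 1 schedules post-baseline Cycle 1 blood counts on Days 3, 8, 15, 22 and 26. A patient who stops for good after Day 19 is left with one EoT visit, due within 14 days of the last dose and possibly before Day 28.
- A patient who has taken nine doses can miss at most three, so the criterion of more than three missed doses can no longer be met.

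The laboratory DLTs matter most here. Anemia is the commonest related event (32 of 47 patients in Protocol Table 11), and one of the two reported DLTs was Grade 4 anemia (Protocol 1.2.1).

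The MTD and RP2D are primary endpoints. Part B starts at a dose cleared in Part A, Part C uses such a dose, and the RP2D is the dose for up to 65 expansion patients.

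**Working it through.** **Inputs.** Dosing days, from Protocol 6.2.5: "Days 1, 3, 5, 8, 10, 12, 15, 17, 19, 22, 24, 26 in a 28-day cycle". DLT window: 28 days. 3+3 rule, from Protocol 6.2.6.1: escalate on 0 of 3, or on 1 of 3 followed by 1 of 6 in total; otherwise stop. True DLT rate: 33%, from Protocol 9.8.

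**Step 1: the unprotected part of the window.** 0.75 × 12 = 9 doses. With none missed, the ninth listed dosing day is Day 19. Days 20 to 28 remain: 28 − 19 = 9 days, and 9/28 = 32%.

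**Step 2: reproduce the plan's figure.** With p the DLT probability and q = 1 − p,

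P(halt) = 1 − [q³ + 3pq² × q³].

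- p = 0.33: 1 − [0.301 + 0.444 × 0.301] = 0.566.
- p = 1/3: 1 − [0.296 + 0.444 × 0.296] = 0.572.

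Both round to the stated 0.57. That figure presumes that the full 28-day risk is seen in every patient.

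**Step 3: the risk seen by Day 19.** The documents do not say when DLTs occur, so this is assumed.

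- Constant hazard, p = 1/3: p′ = 1 − (2/3)^(19/28) = 0.2405 (0.238 for p = 0.33).
- Uniform onset: p′ = p × 19/28 = 0.226 for p = 1/3 (0.224 for p = 0.33).

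**Step 4: one early leaver in the first three** (p = 1/3, constant hazard, q′ = 0.7595).

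- No DLT in three: q²q′ = 0.444 × 0.7595 = 0.338.
- One DLT in three: 2pqq′ + q²p′ = 0.338 + 0.107 = 0.444.
- Clears: 0.338 + 0.444 × 0.296 = 0.469. P(halt) = 0.53.

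**Step 5: one early leaver in each group of three.** The second three now also clear with probability 0.338: 0.338 + 0.444 × 0.338 = 0.488, so P(halt) = 0.51.

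**Step 6: every patient cut at Day 19.** q′³ + 3p′q′² × q′³ = 0.438 + 0.416 × 0.438 = 0.620, so P(halt) = 0.38.

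**Range over both onset assumptions and both values of p:**

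| Patients followed only to Day 19 | P(halt) |
|---|---|
| None | 0.57 |
| One, in the first three | 0.52 to 0.53 |
| One in each three | 0.50 to 0.51 |
| All (worst case) | 0.34 to 0.38 |

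**Sensitivity to timing.** In the worst case, with 10%, 25% or 50% of DLTs falling on Days 20 to 28 (p = 0.33), P(halt) is 0.50, 0.39 or 0.22. The size depends on timing; the direction does not, because truncation can only lose DLTs.

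**The case against.** The best defense is that the surrounding text means the whole cycle. A cycle is 28 days, and the 75% can be read as an exposure floor within a completed cycle. Protocol 6.2.6.1 makes the first escalation depend on no DLT during Cycle 1 and defines the MTD by Cycle 1 DLTs. Sections 6.2.6.1 and 6.2.6.3 base decisions on Cycle 1 toxicity data, and the supportive-care text equates the DLT period with the first 28 days. This stands for patients still on study. A reader might infer from the decision sentence that the plan intends to escalate at Day 19. Read alone, the sentence allows that; read with these passages, it does not show such an intention.

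A reader might also infer that Days 20 to 28 simply go unobserved. They need not. AEs are recorded for 30 days after the last dose unless new therapy starts, which is to about Day 49 for a last dose on Day 19. SAEs are collected for at least 30 days. The EoT visit includes a blood count and chemistry, and laboratory tests continue on schedule if drug is only withheld (Protocol 7.5.4.1). Progression on Day 20 therefore does not by itself end AE capture. What remains exposed is withdrawal of consent, new therapy before Day 28, and sparse blood counts after permanent stopping.

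Protocol 3.2 does not repeat the 75% definition, so it could be read as allowing replacement of a patient who leaves on Day 20. That is a second ambiguity rather than a cure.

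Other safeguards exist: investigators may class further events as DLTs, escalation needs written sponsor confirmation, the RP2D may be set below the MTD, and expansion enrollment is held if DLT-type events exceed 33%. They soften the consequence of a wrong count but do not correct the count.

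**Conclusion.** The point holds as a mismatch between a dose-count denominator and a 28-day event window. It is a stated rule with a one-sided effect, repeated in both documents: nothing requires a DLT-free patient to be followed to Day 28 before being counted.

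The size is modest in the likely case. One early leaver among the first three lowers the probability of halting at a 33% dose by about 0.04, from 0.57 to about 0.53. This rests on an assumed constant hazard and on nothing being learned about that patient after Day 19; whatever later follow-up captures makes the loss smaller.

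A reader might take 0.38 as the design's real halting probability. The documents do not support that: it needs every patient to be cut at Day 19, and they give no DLT timing. It is an upper bound on the damage under that onset assumption, close to the 0.34 that uniform onset gives.

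**What to change.** Amend the synopsis and Sections 3.2, 6.2.6.1 and 9.3.5 of the protocol, and SAP 1.1 and 3.1.2, so that all agree with the 28-day window:

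1. A patient is DLT-evaluable if he or she had a DLT, or received at least 75% of the Cycle 1 KPT-9274 doses and was followed for DLTs to the end of Day 28, with enough safety data to judge DLT status. One missed blood draw does not by itself exclude a patient.
2. A DLT-free patient without that follow-up is non-evaluable and replaceable.
3. The cohort decision is taken after the last evaluable patient has passed Day 28 or had a DLT.

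The second half of item 1 should not be worded as all scheduled assessments through Day 28. The last scheduled Cycle 1 visit is Day 26, and that wording could exclude a fully dosed patient over a single missed sample.

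The cost is a wording change in two documents, an occasional replacement patient, and a wait of up to 9 days (28 − 19) before a cohort decision. No dose or treatment rule changes.

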6.2.6.2. Dose-Limiting Toxicity

A DLT is defined as an AE or abnormal laboratory value that occurs within the first 28 days of treatment with KPT-9274, except for those that are clearly and incontrovertibly due to underlying disease, disease progression, or extraneous causes, and meets any of the criteria included in [Table 14](#). The CTCAE, Version 4.03 will be used for grading. In addition, > 3 missed (consecutive or non-consecutive) doses of KPT-9274 in the first 28 days due to a drug related toxicity will be considered to be a DLT.

Other events may occur which do not meet the definition of a DLT, but are of concern to the Investigators and Karyopharm, and may then be considered to be DLTs.

Table 14: Criteria for Defining Dose-Limiting Toxicities

Toxicity	Any of the following criteria (based on CTCAE [Version 4.03]):
Non-Hematologic	Grade \geq 3 nausea/vomiting, dehydration or diarrhea while taking optimal supportive medications.
	Any other Grade \geq 3 non-hematological toxicity except alopecia or electrolyte abnormalities correctable with supportive therapy.
Hematologic	Grade 4 neutropenia lasting more than 5 days.
	Febrile neutropenia of any duration (ANC $< 1.0 \times 10^9$ with single temperature $> 38.3^{\circ}\text{C}$ or a sustained temperature $\geq 38^{\circ}\text{C}$ for more than 1 hour).
	Grade 4 thrombocytopenia, or Grade 3 thrombocytopenia with bleeding, or any requirement for platelet transfusion.
	Grade 4 anemia, unexplained by underlying disease.

CTCAE Version 4.03 will be used for grading AEs and laboratory abnormalities. Patients may receive supportive care as per local institutional guidelines.

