6.2.8. KPT-9274 Dose Reduction Guidelines for Toxicity

For Grade 2 toxicities present at baseline, the drug will not be held and the treating investigator will closely monitor and support the patient.

Patients are expected to be aggressively treated to minimize the likelihood and/or severity of side effects at the discretion of the Investigator (consultation with the Karyopharm Medical Monitor is strongly encouraged), particularly GI symptoms and hematopoietic toxicities as observed in KPT-9274 animal toxicology studies. See Section [6.9.1](#) for supportive care details.

For patients who do not tolerate the protocol-specified dosing schedule, KPT-9247 dose adjustments are permitted in order to allow the patient to continue the study treatment. The criteria for dose modifications of KPT-9274 for toxicities are outlined in [Table 15](#). These changes must be recorded on the eCRF. If a patient requires a dose delay of more than 28 days (> 28 days) from the intended day of the next scheduled dose, then the patient should be discontinued from the study (in exceptional situations, if the patient is clearly benefiting from the study treatment, and in the opinion of the Investigator no safety concerns are present, after discussion with the Karyopharm Medical Monitor, the patient may remain in the study).

If, after interruption of treatment and resolution of the event, treatment is resumed at the same dose and the same toxicity reoccurs with the same severity, the next treatment re-initiation must resume at the next lower dose level, irrespective of duration. Patients who do not recover (i.e., ≤ Grade 1 or baseline) within 28 days (≤ 28 days) of discontinuation of study treatment will not be permitted to re-start study treatment and will be discontinued from the study.

In the event of a DLT (Cycle 1) during the Dose Escalation Phase the patient must discontinue KPT-9274.

In the event of any other toxicity (< Grade 3) during the Dose Escalation Phase, one of the following actions may be taken at the Investigator's discretion after consulting with the Karyopharm Medical Monitor:

- Patients can continue treatment with KPT-9274 without a dose delay or reduction.
- If the decision is made to hold KPT-9274:

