\geq Grade 3	
Optimal supportive care medications according to institutional guidelines or NCCN Clinical Practice Guidelines in Oncology should already be instituted. Also refer to Benson Guidelines.
 
Hold KPT-9274 until the event resolves to \leq Grade 1 or baseline (as appropriate):
 
 First occurrence of \geq Grade 3: 
 If supportive care results in the AE improving to Grade \leq 1 or baseline within 3 days (\leq 3 days), restart KPT-9274 at the current dose. If the improvement to Grade \leq 1 or baseline takes longer than 3 days ($>$ 3 days), KPT-9274 should be resumed at one dose level lower (see Table 15). Second or greater occurrence of \geq Grade 3, restart KPT-9274 at one dose level lower (see Table 15) upon improvement to Grade \leq 1 or baseline irrespective of duration. 
**If the toxicity does not resolve to \leq Grade 1 or baseline within 28 day (\leq 28 days), study treatment will be discontinued permanently.
 
**If, after interruption of treatment and resolution, treatment is resumed at the same dose and the same toxicity reoccurs with the same severity, next treatment re-initiation must resume at the next lower dose level, irrespective of duration.

Toxicity and Intensity	Dose Modification
Hematological Toxicity	
Thrombocytopenia	
Grade 2	Maintain dose

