\geq Grade 3	
Implement growth factors and broad anti-microbial coverage per institutional guidelines.
 
Transfusions (e.g., RBCs for anemia) are allowed per institutional guidelines.
 
Consider holding KPT-9274 until the event resolves to Grade \leq 1 or baseline and restart at one dose level lower (see Table 15). At the discretion of the Investigator after consulting with the Karyopharm Medical Monitor, patient may be treated with KPT-9274 without dose delays or modifications while receiving transfusions and/or growth factor support per institutional guidelines.

All dose modifications should be based on the worst preceding toxicity.	
*Isolated values of \geq Grade 3 alkaline phosphatase values will NOT require dose interruption. Determination of liver vs. bone etiology should be made, and evaluation of gamma-glutamyl transferase (GGT), 5'-nucleotidase (5'NT), or other liver enzymes should be performed.	
Note: for combinations of Grade 1 or 2 adverse events (e.g., nausea, fatigue, anorexia) that significantly impair the patient's quality of life, 1-2 doses of study treatment may be skipped after consultation with the Karyopharm Medical Monitor and supportive care per institutional guidelines has been implemented. Study treatment may then be restarted after consultation with the Karyopharm Medical Monitor.	
Benson AB, Ajani JA, Catalano RB, et al.	

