6.2.8.1.1. Conditions Not Requiring KPT-9274 Dose Reduction

The following conditions are exceptions to the dose-modification guidelines. KPT-9274 does not need to be held in the following cases:

- Alopecia of any grade.
- Electrolyte or serum analyte (e.g., urate) abnormalities that are reversible with standard interventions.

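### In Cycle 1 of dose escalation the protocol both requires and waives stopping KPT-9274 for certain isolated Grade 3 or higher laboratory values

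*Protocol*

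**What the plan says.** **What counts as a DLT.** Section 6.2.6.2 opens: "A DLT is defined as an AE or abnormal laboratory value that occurs within the first 28 days of treatment with KPT-9274". It leaves out events by cause, "except for those that are clearly and incontrovertibly due to underlying disease, disease progression, or extraneous causes", and then points to Table 14. The relevant row of Table 14 takes in any other Grade 3 or higher "non-hematological toxicity except alopecia or electrolyte abnormalities correctable with supportive therapy". Neither alkaline phosphatase nor urate is named. The synopsis carries the same table.

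**What follows from a DLT.** Section 6.2.8: "In the event of a DLT (Cycle 1) during the Dose Escalation Phase the patient must discontinue KPT-9274". Section 5.2 adds that a patient whom the investigator takes off treatment may not go back on it.

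**What the dose-modification text says.** The note under Table 16, on isolated values at or above the grade, reads "Grade 3 alkaline phosphatase values will NOT require dose interruption", and asks for a work-up of liver against bone origin. Section 6.2.8.1.1 states: "The following conditions are exceptions to the dose-modification guidelines. KPT-9274 does not need to be held in the following cases". Its list includes "Electrolyte or serum analyte (e.g., urate) abnormalities that are reversible with standard interventions". Neither passage is limited by cycle or by study phase.

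**How the count is used.** Section 6.2.6.1 applies 3+3 rules to 3 or 6 patients. No DLT in 3 leads to escalation, 1 in 3 leads to expansion to 6, and 2 or more in 3 or in 6 means that the MTD has been exceeded. Section 9.8 bases the MTD on Cycle 1 DLTs.

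**The concern.** The list of what is not a DLT is shorter than the list of what needs no hold. Alkaline phosphatase and non-electrolyte analytes such as urate fall in the gap. An investigator with such a value in Cycle 1 of escalation finds one passage that ends treatment for good and another under which dosing simply continues.

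Such values will be looked for. Table 19 puts both analytes in the chemistry panel, and Table 1 schedules that panel on Days 3, 8, 15, 22 and 26 of Cycle 1. The entry criteria in Section 4.2 limit bilirubin, AST and ALT but set no limit on alkaline phosphatase.

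Two things are at stake. One is whether an individual patient stays on drug. The other is whether all sites and dose decision meetings classify the same event in the same way. A site that relies on the no-hold text could continue dosing and not raise the value as a DLT. In cohorts of 3 or 6, one such event turns 0 of 3 into 1 of 3, or 1 of 6 into 2 of 6.

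**Working it through.** **Step 1: follow one value through the text.** Take an isolated Grade 3 alkaline phosphatase value in Cycle 1 of escalation, not clearly due to disease or another cause.

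- Section 6.2.6.2: it is an abnormal laboratory value within 28 days, non-hematologic and Grade 3, and neither alopecia nor an electrolyte change. It is a DLT.
- Section 6.2.8: a Cycle 1 escalation DLT means discontinuation.
- Table 16 note: no interruption is needed.

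A Grade 3 urate value that can be reversed takes the same path, with Section 6.2.8.1.1 in place of the note. The second and third instructions cannot both be carried out.

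**Step 2: look for a rule of precedence.** There is none. Section 6.2.6.2 lets the team add events as DLTs but gives no route to remove one that qualifies. The exclusion by cause needs certainty, and the Table 16 note itself implies that the origin may be unknown when the value appears.

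**Step 3: reproduce the plan's own figure.** With DLT probability p and q = 1 − p, escalation continues after 0 of 3, or after 1 of 3 followed by 0 of 3:

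P(halt) = 1 − q³ − 3pq² × q³

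Section 9.8 gives 0.57 at a true rate of 33%. At p = 0.33, q³ = 0.3008 and 3pq² = 0.4444, so P(halt) = 1 − 0.3008 − 0.1337 = 0.566. At p = 1/3 it is 0.572. The stated figure reproduces.

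**Step 4: sensitivity to classification.** The documents give no rate for these laboratory events. Assume rate a, independent of other DLTs, so that p_total = 1 − (1 − p)(1 − a). Example: p = 0.10 and a = 0.05 give p_total = 1 − 0.90 × 0.95 = 0.145 and P(halt) = 0.176.

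| Rate of other DLTs | Values not counted | Counted, a = 2% | a = 5% | a = 10% |
|---|---|---|---|---|
| 10% (assumed) | 0.094 | 0.125 | 0.176 | 0.270 |
| 20% (assumed) | 0.291 | 0.326 | 0.379 | 0.464 |
| 33% (Section 9.8) | 0.566 | 0.591 | 0.628 | 0.686 |

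The rise is about 3 to 18 points. A cohort of 3 would contain at least one such event with probability 1 − 0.95³ = 0.143 at 5%, or 1 − 0.90³ = 0.271 at 10%.

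**Step 5: the same from the pooled observed rate.** Section 1.2.1 reports 2 DLTs in 47 patients, so p = 2/47 = 0.043 and P(halt) = 0.02. Adding an assumed 3% or 5% gives p_total = 0.071 or 0.090, and P(halt) = 0.05 or 0.08.

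**The case against.** The strongest reply is that the two sets of passages do different jobs. Table 14 says what is a DLT. The Table 16 note speaks only of interrupting the dose, and Section 6.2.8.1.1 calls its items exceptions to dose modification. Neither says that such a value is not a DLT. This stands. A reader might infer that the protocol holds two rival DLT definitions and that the MTD depends on which page is followed. The documents do not support that: read literally, the count comes from Table 14 and its synopsis copy alone.

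It can also be argued that Table 16 is the general schedule and the Cycle 1 sentence a specific override. The general Grade 3 or higher non-hematologic row of Table 16 also departs from the DLT rule: it holds the drug and, on quick recovery, says "restart KPT-9274 at the current dose". Appendix 6 records the Cycle 1 sentence as introduced so that no patient resumes drug after a DLT. The reading is coherent, but the protocol never states it, and the no-hold passages carry no Cycle 1 exception.

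Third, dose decision meetings review all laboratory abnormalities, whether or not assessed as DLTs (Section 6.2.6.3). This lowers the risk of a missed event but does not say how to classify one.

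Finally, the two reported DLTs were Grade 4 anemia and Grade 3 fatigue, and Table 11 lists neither alkaline phosphatase nor urate. That gives the 10% scenario no support. It does not show that such values were absent, because Table 11 covers only treatment-related events in at least 10% of patients.

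**Conclusion.** The contradiction is real and narrow. It concerns a Cycle 1 dose-escalation patient with an isolated Grade 3 or higher alkaline phosphatase value, or a Grade 3 or higher serum analyte value that can be reversed, where disease or another cause does not clearly explain it. For that patient one passage requires permanent discontinuation and another waives any interruption.

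For DLT counts and the MTD the consequence is a risk of inconsistent classification. Its size is unknown. The rises of 3 to 18 points rest on assumed event rates, assumed independence and, in two rows, an assumed rate of other DLTs. No affected cohort is shown.

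A reader might also infer that the conflict carries into expansion. The discontinuation conflict does not. The mandatory stop is limited to Cycle 1 of escalation. In expansion, Section 6.2.8 counts DLT-type events towards a hold on enrollment above 33% of patients, and a value can count there while that patient's dosing continues. What does carry over, to that count and to Part C (Section 3.1), is the DLT definition and so the need to apply it in one way.

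**What to change.** Reconcile Table 14, the synopsis DLT table, the Cycle 1 sentence in Section 6.2.8, the Table 16 note and Section 6.2.8.1.1. State two things explicitly: which passage governs in Cycle 1 of escalation, and whether these laboratory values count as DLTs. The clinical content is for the sponsor to decide, and nothing here presupposes that the values are exempt or that they count.

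Before the next dose decision, check the Cycle 1 Grade 3 or higher laboratory values already collected, and confirm that they were classified for DLT purposes in the same way across sites and cohorts.

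The cost is protocol wording and a short review of existing data. Sample size and the 3+3 rules are unaffected.
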